SAE	Serious Adverse Event	
SDV	Source Data Verification	
SOP	Standard Operating Procedure	
TMF	Trial Master File	

STUDY OVERVIEW		
Full title	Management of Patients with Chronic Liver Disease (CLD) admitted	
	to Hospital as an Emergency.	
Objectives	 To evaluate the impact of different patterns of service organisation, provision and delivery in the English NHS on patient care and outcomes. To identify processes of care that may be used to address the 	
	existing marked inequalities in health, improve patient experience, engagement with healthcare and survival.	
Type of trial	Mixed methods project: this application and protocol relates to quantitative data linkage work package.	
Trial design and methods	This quantitative component will use linked national datasets in combination with a detailed characterisation of general and specialist liver and critical care service provision and practice to study determinants of received care and clinical outcomes of CLD patients after a first emergency admission (EA), in the study period between 1 April 2009 and 31 March 2022 in the English NHS.	
Health condition(s) or problem(s) studied	Emergency hospital admissions of people with CLD.	
Target sample size	Data on approximately 100K subjects	
Trial duration per	Not applicable.	
participant:		
Main inclusion/exclusion criteria:	All adult patients with CLD with a first emergency hospital admission in the study period from 1 April 2009 to 31 March 2022 according to HES-APC data and classified according to ICD-10 diagnostic codes. Data from people who have chosen the National Data Opt-Out will be excluded from the study cohort.	
Statistical methodology	Multiple methods to be utilised: please see statistics plan in section	
and analysis:	9.	
STUDY TIMELINES	2 vears	
Study Duration/length	2 years	
Expected Start Date	01/09/2022	
End of Study definition and anticipated date	Completion of planned analyses and submission of final report. 01/09/2024	
Key Study milestones	Funding already awarded. REC approval 1/09/2022	
STORAGE of SAMPLES (if applicable)		
Human tissue samples	Not applicable	
Data collected / Storage	Only existing data will be used in this part of the study. All data	
	analysed will be de-identified at source. All storage and analysis of the	
	de-identified dataset will be at the London School of Hygiene and Tropical Medicine (LSHTM).	

NHS Foundation Trust

1 INTRODUCTION

Liver disease is a serious and increasing health problem in the UK. However, people with liver disease often do not know that they are affected until they need to be admitted to hospital as an emergency. These people are often very ill, and a quarter of them die within two months of coming into hospital. The care they get when they are in hospital, and after being discharged, varies greatly across the country. This variation in care has major effects on how long they survive. Survival of those who live in the most deprived areas is half that of those who live in the most well-off ones. We want to understand how and why the place where people live and the care that is available to them affect the way they are treated and their survival. We also want to see how variation in outpatient care after discharge makes a difference. Through this research we hope to understand what clinical practices have the best results and how we can guarantee that they are delivered across the country.

To do this research, we will gather very detailed information about the arrangements for care given to people with liver disease in each hospital in England and then use the health information routinely recorded when people are treated in these hospitals. Information from different parts of the NHS will be 'linked' together into a single database so we can analyse the complete course of people's illness. Data analysed by the research team will have names and all other identifying information removed. We will analyse data from more than 100,000 people with liver disease who had emergency admissions to NHS hospitals in England over more than a decade.

2 BACKGROUND AND RATIONALE

The increasing prevalence of liver disease in the UK, the resulting increase in morbidity and mortality, and the regional variation in survival has been extensively reviewed in reports of the Lancet Commission on Liver Disease in the UK and the Atlas of Variation in Risk Factors for Liver Disease in England (1,2). Below we summarise these reports as well as evidence from an extended review of the literature that was carried out to support this application. This review highlighted serious questions about the current provision and delivery of care for patients with CLD, especially in patients who were admitted to hospital as an emergency.

Mortality rates from CLD in the UK have increased 400% since 1970, and in people younger than 65 years have risen almost five-fold (1,2). Most patients die in working age and CLD is now the third biggest cause of premature mortality. In 2018, liver disease was the leading cause of death for those age 35-49 years. However, the prevalence of liver disease and its outcome is not uniform across the UK. Studies in England have shown wide variation: premature mortality varies 7.7-fold and hospital admissions 8.5-fold by Clinical Commissioning Group (CCG). This variation is closely linked to the level of socio-economic deprivation. People with CLD who live in the most deprived areas of England die nearly 10 years earlier and have a mortality rate that is twice as high compared to those who live in the most affluent ones (1,2).

CLD has a wide range of different aetiologies. People with CLD, particularly if it is alcohol-related, often first come to medical attention with an unplanned emergency admission (EA) to hospital when their disease is already advanced. Over a quarter of these patients die within 60 days of their first EA (3,4). Re-admissions are common and associated with a worse prognosis, and nearly 70% of patients who survive a first EA will die within 5 years (3).

Provision of specialist care for people with CLD admitted as emergencies shows wide variation across the UK with major imbalances between service provision and local disease burden (5). A study of CLD patients admitted to hospital between 2004 and 2012 in England and Wales suggested that early input

King's College Hospital MHS

NHS Foundation Trust

of liver specialists – hepatologists or gastroenterologists – may improve patient care and is associated with a reduction in early mortality by more than 20% (3). However, more recent evidence indicates that specialist care is still lacking, with very few districts general hospitals having dedicated hepatology services, and very limited provision for out-of-hours or weekend care (6).

An evidence-based care bundle ('BASL Care Bundle') has been developed for the early care of patients with CLD after being admitted as an emergency. An evaluation in seven hospitals in North West England shows that the care bundle's introduction may be associated with reduced mortality in "outlier hospitals", but it has not been evaluated elsewhere (7,8).

People with CLD are often severely ill when first admitted and up to a third may require transfer to a high-dependency unit (HDU) or ICU for "critical care" support. However, there is variation in ICU admission rates and not all receive the critical care that they may benefit from, particularly if their CLD is alcohol-related (9,10). A National Confidential Enquiry into Patient Outcome and Death (NCEPOD) review of deaths in patients with alcohol-related CLD identified systematic stigma and linked mortalities (9). Appropriate escalation of care with ICU admission often did not occur, even if indicated, and when a patient had been admitted, treatment was often inappropriately limited or withdrawn. Nihilism is not justified as ICU survival for CLD in England has shown progressive improvement (11).

After hospital discharge, continued input from liver specialists is also important. Research from outside the UK suggests that prompt, coordinated specialist outpatient review is associated with lower readmission rates, healthcare costs and improved survival (12-15). In the UK, care and support for outpatients with CLD are poorly characterised but appear very variable. For example, in people whose CLD is severe, referral to liver transplant (LT) centres by local specialists for possible LT is key but there is a more than 5-fold difference in the rates of LT between CCGs – a difference that does not correlate with local prevalence of CLD (2).

Evidence explaining why this research is needed now

Since 2014, the Reports of the Lancet Commission into Liver Disease in the UK have raised concerns about the increasing mortality from CLD, particularly after an EA, drawing attention to the marked regional variation in survival and of the limited and unequal provision of the specialist care.

There is a need to re-configure the currently limited UK services so that they deliver care associated with the best possible outcomes in a consistent way across the country. UK-based initiatives to address these shortfalls have been proposed but to date their adoption has been patchy and their large-scale and long-term effects are unknown. These initiatives include the care bundle developed by the British Association for the Study of the Liver (BASL) and NICE Pathways as well as the recent recommendation for regional liver centres linked to a hub-and-spoke network of surrounding district general hospitals (16). Wider initiatives to re-configure clinical services for maximum benefit for this often disadvantaged patient group – particularly in relation to outpatient care – have not been tested in the NHS.

It is currently difficult to establish which processes of care improve patient outcomes because data on different aspects of care are collected in different datasets or data are simply unavailable. Linking national datasets at patient level – and supplementing this with key novel information on the configuration of services – will provide for the first time a rich source of detailed clinical information

King's College Hospital NHS

NHS Foundation Trust

about the about 9,000 people with CLD having a first EA each year. By mapping processes and outcomes of patients over time, across hospitals and between clinical networks, we have a unique opportunity to disentangle the factors related to the organisation and delivery of liver services, derived from our mapping of existing health service characteristics, and those related to particular processes of care derived from the analysis of national linked datasets as detailed in this protocol, that have the greatest impact on patient outcomes.

There is also an urgent need to investigate the currently poorly characterised stigma that confronts many people with CLD once admitted to hospital and the difficulties of engagement with healthcare that result. In a separate work package of the same research project, ethnographic observations of liver care services and interviews with CLD patients will inform how liver service can be designed best to meet CLD patients' needs, so that they can benefit from timely escalation of care or referral for liver transplantation. The findings of the social science work package (which will be the subject of a separate protocol) will inform this quantitative work package Our proposed research project provides an opportunity to develop a systematic approach to re-configure liver services available in the NHS, specifically confronting the stigma and disadvantage experienced by many CLD patients, in order to strengthen their engagement with healthcare.

3 OBJECTIVES

3.1 Primary Objective

The overall aim is to identify which characteristics of treatments and services for acutely ill people with CLD impact on care processes and outcomes.

The project will investigate:

1. Time trends in acute secondary care use for patients with CLD and their outcomes.

2. Regional variation in acute secondary care use for patients with CLD and their outcomes.

3. The impact of regional clinical networks on referral and transfer patterns.

4. The impact of regional, hospital and patient characteristics on critical care use of CLD patients who had a first EA.

5. The impact of regional, hospital and patient characteristics on use of liver transplantation after a first emergency hospital admission in patients with CLD.

6. The impact of coordinated specialist outpatient review after discharge on readmissions, referral for transplantation, and mortality.

Our analyses will also seek to assess the impact of the Covid-19 pandemic on all these aspects of care.

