7.2 Exclusion Criteria

A previous emergency hospital admission with chronic liver disease in the two preceding years.

People who have chosen to adopt the National Data Opt-Out.

8 **RECRUITMENT**

Not applicable: study working with existing routine data only.

A data flow diagram is appended as Appendix 2.

Hospital Episode Statistics (HES) data will be requested from NHS Digital for patients with a Chronic Liver Disease (CLD) diagnosis anywhere in their episodes in the study period (1 April 2009 to 31 March 2021). CLD diagnosis will be defined as ICD-10 codes in the range between B15-B19 or between K70-K77.

Analysts at NHS Digital will identify the patient cohort. They will send the identifiers of these patients (without any clinical data) to the Intensive Care National Audit and Research Centre (ICNARC) for linkage to ICNARC data.

Patients undergoing a liver transplant in England between one year before the study period to one year after the study period will be identified in The UK Transplant Registry, by NHS Blood and Transplant. The identifiers of these patients will be sent (without clinical data) to NHS Digital for linkage to HES.

De-identified cohorts of patients will be sent from NHS Digital, ICNARC and NHS Blood and Transplant to LSHTM for analysis, containing no patient identifiers. Pseudonymised study IDs will be used by the research team at LSHTM to link the three datasets.

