9 STATISTICAL METHODS

Please see section 4 above. Further, an overview of the statistical plan is presented below.

King's College Hospital NHS

NHS Foundation Trust

We will include all patients older than 18 years with chronic liver disease (CLD) who were admitted with a first emergency admission (EA) in the study period from 1 April 2009 to 31 March 2022. Patients will be considered to have CLD if they have a Hospital Episode Statistics (HES) inpatient record with an ICD-10 codes in the range between B15- B19 or between K70-K77. An EA will be identified based on an administrative HES code related to the method of admission. We will consider an EA to be a first-time occurrence if there is no record of a similar admission, with a minimum of in two preceding years of data available (the "look-back" period).

We will create coding schemes that describe the clinical characteristics of the patients, including the nature and severity of the CLD, their comorbidities, and their adversity-related health issues. Coding schemes will also be developed to capture critical care admissions, predominantly based on data items available through linkage with Intensive Care National Audit and Research Centre (ICNARC) data but enhanced by also including information available in HES records of hospital admission and adult critical care episodes. In addition, we will derive measures that capture specific patterns of secondary care use in the year immediately after the first EA, in terms of the number of planned outpatient visits, and A&E attendances, the number of planned and emergency readmissions, and the total time spent in hospital.

Specific research questions:

1. Time trends in acute secondary care for patients with chronic liver disease and its outcomes:

We will use the linked datasets to describe for each year in the study period from 1 April 2009 to 31 March 2022, the number of CLD patients who had an EA, the proportion of these patients who had an admission to critical care and its duration, total length of hospital stay, readmission rate and total time spent in hospital within the first year, the rate of liver transplantation, and in-hospital and 1-year mortality. Changes in these results over time (including changes in the period 2020-2022 as a result of the Covid-19 pandemic) will be determined with Poisson, logistic or linear regression models, depending on the nature of the dependent variable.

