4. Impact of regional, hospital and patient characteristics on critical care use of chronic liver disease patients who had a first emergency admission: We will explore the association between which of the regional characteristics (e.g., network arrangements, prevalence of CLD, use of transplantation), hospital characteristics (e.g., transplant centre status, specialist staffing, ICU capacity, ICU case-mix), and patient characteristics (e.g., type of CLD and comorbidity, age, sex, socioeconomic deprivation) are associated with the proportion of cases admitted to critical care, their clinical condition at critical care admission, the duration of critical care, and the proportion of cases for whom critical care was withdrawn. We will also explore changes in critical care use as a result of the Covid-19 pandemic. Multilevel logistic regression models will be used to estimate adjusted odd ratios that capture the impact of the regional, hospital and patient characteristics and the Covid-19 pandemic on critical care use.

5. Critical care use and clinical outcomes after a first EA in patients with CLD: We will characterise hospitals according to the proportion of patients that are admitted to critical care and whether they were admitted to critical care early or late in order to explore to what extent hospitals with more frequent and earlier critical care admissions of CLD patients after an EA have better short-term outcomes (in-hospital mortality and readmissions, total time spent in hospital and mortality during the year following the EA). The results will be analysed using multilevel logistic regression including the level and timing of critical care use as hospital-level characteristics with adjustment for key patient characteristics, including age, sex, socioeconomic deprivation, and comorbidity.

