Physical risk – Patients may find a long interview tiring. In addition, some people with CLD may be immunocompromised, and individuals with CLD have a higher rate of mortality from COVID19 than those without CLD.

Mitigation: Interviews will be conducted at a time and place that suits the interviewee. For clinical staff and inpatients, this will depend on the possibilities available in the different hospital sites. For outpatients, interviews may take place in the participant's home, over the phone or in clinics,

depending on what interviewees prefer. The project will operate with reference to the situation of COVID-19 at the time of the study. If meeting in person, researchers experiencing COVID-19 symptoms will test themselves for COVID-19 using lateral flow tests for the two days before the interview. The research team will continue to review the position of COVID-19 and any new variants in the UK and introduce other measures, such as remote interviewing, where necessary.

Professional conflict of interest – For observing or interviewing clinicians, there is a potential for professional conflicts of interest, if they feel invited to report on clinical practices they do not agree with.

Mitigation: The project researcher will emphasise that the purpose of the study is not to discover or report poor quality practice, and that if concern does arise for staff participants they should follow Trust guidelines and support.

Risk of disclosure of harm – There is a risk that participants may disclose an intention to harm themselves or others.

Mitigation: The project has asked clinicians selecting potential participants to exclude individuals who may pose a risk to themselves or others. If this situation arises, participants will notify clinical staff in the patient's hospital, whilst taking care to maintain confidentiality regarding other topics discussed in the interviews.

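### The 2020-22 pandemic contrasts estimate a total effect and cannot separate Covid-19 infection from changes in liver care

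*Protocol*

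**What the plan says.** **Objective.** After listing six topics on care use, networks, transplantation and outpatient review, section 3.1 adds: "Our analyses will also seek to assess the impact of the Covid-19 pandemic on all these aspects of care".

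**Cohort.** Section 9 of the protocol states: "Patients will be considered to have CLD if they have a Hospital Episode Statistics (HES) inpatient record with an ICD-10 codes in the range" B15-B19 or K70-K77. It also states: "An EA will be identified based on an administrative HES code related to the method of admission". Section 7.2 has two exclusions: "A previous emergency hospital admission with chronic liver disease in the two preceding years" and "People who have chosen to adopt the National Data Opt-Out". Neither concerns Covid-19. The patient coding described in sections 4 and 9 covers the nature and severity of the liver disease, comorbidities and adversity-related problems; Covid-19 infection is not named.

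**Contrast.** In section 9, question 1 looks at changes over 2020-2022 and attributes them to the pandemic. Question 2 assesses the pandemic's impact on regional variation in admission rates and outcomes. Question 4 promises "adjusted odd ratios that capture the impact of the regional, hospital and patient characteristics and the Covid-19 pandemic on critical care use". Question 6 asks whether transplantation patterns changed in response to the pandemic. None of the four separates admissions with Covid-19 from those without.

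**The concern.** A person with coded cirrhosis who was admitted as an emergency with Covid-19 pneumonia in 2020-22 can meet every stated criterion. Such a patient's critical care use and survival reflect the infection at least in part. A comparison of 2020-22 with earlier years then combines two things: a new acute illness entering the cohort, and any change in how liver patients were admitted, escalated, transplanted or followed up.

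The objective is worded as impact on care, and section 20 sends the findings to commissioners and to NICE. If the two parts are not separated, deaths from infection could be read as worse liver care, and infection-driven admissions could hide part of a fall in liver-driven ones. The mixing could also differ between regions with different infection rates, which bears on question 2.

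**Working it through.** The plan states no figure to reproduce, so the question is first one of definitions and then of plausible size.

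**Definitions.** Set side by side, section 9 fixes entry by liver code and admission method, section 7.2 removes nobody for Covid-19, and questions 1, 2, 4 and 6 contrast calendar periods. Nothing named in the protocol distinguishes infection from service change.

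**Inputs from the protocol.** Section 2 gives about 9,000 first emergency admissions a year and a 60-day mortality of just over a quarter. April 2009 to March 2020 is 11 years: 11 x 9,000 = 99,000 admissions. April 2020 to March 2022 is 2 years: 2 x 9,000 = 18,000. The planned mortality outcomes are in-hospital and 1-year; the 60-day figure serves here only as a baseline.

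**Assumed inputs (not in the documents).** Covid-coded share c of 2020-22 index admissions: 2-10%. Mortality: 25% without and 40% with Covid-19. No change in liver care. Clustering ignored.

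**Mortality.** p = (1 - c) x 0.25 + c x 0.40. OR = [p/(1 - p)] / (0.25/0.75). SE(log OR) = sqrt[1/(18,000 p(1 - p)) + 1/(99,000 x 0.25 x 0.75)].

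| c | p | OR | z |
|---|---|---|---|
| 2% | 0.2530 | 1.016 | 0.9 |
| 5% | 0.2575 | 1.040 | 2.1 |
| 10% | 0.2650 | 1.082 | 4.3 |

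The difference detectable with 80% power (two-sided 5%) is about 1.0 percentage point. The shifts above are 0.3, 0.75 and 1.5 points, and they would reach significance with probability of about 14%, 57% and 99%.

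Section 8 ends the HES request on 31 March 2021, while sections 4, 7.1 and 9 give 31 March 2022. If only one pandemic year (9,000) is available, z is about 1.6 at a 5% share and 3.1 at 10%.

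**Admission counts.** Assume liver-driven admissions fall 10%, from 9,000 to 8,100, and no Covid-coded admission is liver-driven. The observed total is 8,100/(1 - c):

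- c = 2%: 8,265, an apparent fall of 8.2%.
- c = 5%: 8,526, an apparent fall of 5.3%.
- c = 10%: 9,000, no apparent fall.

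Now take c = 5% and suppose that half of the 426 coded admissions (213) were in fact liver-driven. Liver-driven admissions are then 8,100 + 213 = 8,313, a true fall of 7.6%. The all-admissions contrast shows 5.3%, and excluding every coded admission shows 10%. The two versions bracket the truth, and neither equals it.

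No comparable figure can be given for critical care, transplantation or regional variation without further assumptions.

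**The case against.** The strongest reply is that infection is part of the pandemic. A calendar contrast estimates the pandemic's total effect, and harm arises only if a reader draws a service conclusion from it. This stands: the all-admissions contrast is legitimate and should stay. It does not settle the matter, because the objective is worded as impact on care and the protocol does not say that the total effect is meant.

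A second reply is that section 9 calls itself an overview, that coding schemes are still to be developed, and that a code list with a repeat analysis belongs in the statistical analysis plan. The analysis plan or the comorbidity coding may indeed supply the flag, and the absence of a code list is not the complaint. The protocol itself fixes the cohort, the contrast and the attribution to the pandemic, and these together create the ambiguity.

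Four stronger readings are tempting but unsupported:

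- A reader might infer that the index admission may carry a liver code in any position, because section 8 requests data on "patients with a Chronic Liver Disease (CLD) diagnosis anywhere in their episodes in the study period". That sentence governs the data request. Elsewhere the protocol speaks of admissions for or with CLD and leaves the code position open.
- A reader might take the Social Science protocol, section 8.1, as evidence that Covid-19 raises mortality in this cohort: "individuals with CLD have a higher rate of mortality from COVID19 than those without CLD". It compares people with and without liver disease, not liver inpatients with and without Covid-19, so it does not support 40% against 25%.
- A reader might infer that infection must have raised critical care use. That is plausible, but the documents give no figure.
- A reader might conclude that the Covid-excluded contrast should be the only basis for statements on liver care. Exclusion selects on a consequence of the pandemic, in one period only, and can remove liver decompensation with incidental or hospital-acquired infection.

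**Conclusion.** The point holds as one of separation and labelling. As defined in section 9, the 2020-22 contrasts in questions 1, 2, 4 and 6 are total effects that cannot divide infection from changes in liver care. It does not follow that these contrasts are invalid, or that an infection-free version should replace them.

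The size rests wholly on assumed inputs. Over a 2-10% share, with 25% against 40% mortality, the spurious odds ratio runs from negligible (about 1.02) to about 1.08, and the z-values are upper figures because clustering is ignored. The admissions example, 10% appearing as 5.3% at a 5% share, further assumes that no coded admission was liver-driven. The pandemic assessment is an addition to the main aims. Even so, the ambiguity is cheap to remove and bears on recommendations, so the change is worth making.

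**What to change.** 1. State in sections 3.1 and 9 that the all-admissions contrast for 2020-22 estimates the total effect of the pandemic, and keep it.
2. Flag Covid-19 diagnosis codes in the index admission by position, primary or secondary.
3. Repeat the pandemic contrasts in questions 1, 2, 4 and 6 twice: excluding admissions with Covid-19 as the primary diagnosis and, separately, excluding any Covid-coded admission.
4. Attribute a change to liver care or services only when it is consistent across the three versions, and report them as a range.
5. Reconcile the end date of the HES request in section 8 with the study period given elsewhere, since it decides whether the second pandemic year is available.

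The cost is one code list and two repeats of planned models, on HES records already requested. There are two downsides to state with the results. Coding in early 2020 may be incomplete, so the separation is weaker there. Exclusion also conditions on a consequence of the pandemic and may remove some liver-driven admissions, which is why no excluded version should replace the total effect.
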